- number of subjects experiencing bronchospasm clinically or spirometrically determined following IMP administration at the start and end of treatment;
- CCI [redacted] as determined by *in-vitro* CCI [redacted] from Screening/Randomisation (Visit 1/Visit 2) to Visits 3, 5 and end of treatment (Visit 7) as well as on CCI [redacted] from Exacerbation Visits and clinic visits due to pneumonia;
- emergence of other CCI [redacted] and any developing resistance in CCI [redacted] from Screening (Visit 1) to End of Treatment (Visit 7);
- haematology, clinical chemistry and renal function tests;
- physical examination and vital signs data;
- 12-lead electrocardiogram.

Statistical Analysis:

Primary analyses will be performed on the modified intention-to-treat (mITT) population with exclusions from the ITT defined and justified in the Statistical Analysis Plan (SAP). A supportive analysis will be conducted using a per-protocol (PP) population excluding subjects with major protocol deviations.

Annual pulmonary exacerbation rates will be compared between treatment groups using a Poisson regression model allowing for over-dispersion and also considering pooled site, use of stable concomitant therapy with oral macrolides and pulmonary exacerbation frequency in the 12 months preceding Visit 2 as covariates.

The primary analyses detailed above will be a comparison of colistimethate sodium against placebo at the end of the 12-month, double-blind phase. Full details will be provided in the SAP.

The secondary variable of the CCI [redacted] will be analysed using a log-rank test comparing two survival curves. The number of CCI [redacted] will be analysed using an appropriate non-parametric test. The number of CCI [redacted] will also be analysed using a binomial regression model. The absolute changes in CCI [redacted] and the number of days of CCI [redacted] will be presented separately.

CCI scores (CCI total score and CCI [redacted]) will be analysed using linear mixed models.

An analysis of covariance model on log₁₀ transformed values fitting baselines will be used to compare CCI [redacted] between treatment groups.

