19.4.2. EFFICACY DATA

The primary analysis will be performed on the mITT population. Analyses conducted using the PP will be considered supportive.

CCI [REDACTED]
 CCI [REDACTED] will be calculated as the time in days from the date of the first dose of IMP. CCI [REDACTED]
 A log-rank sum test will be used to compare the treatment groups. Subjects completing the trial without CCI [REDACTED] or who are discontinued prematurely CCI [REDACTED], will be considered as censored at the time of their last follow-up.

CCI [REDACTED]
 CCI [REDACTED] will also be presented by treatment group. An appropriate non-parametric test will be used that makes allowing for the effect of prognostic covariates possible. This will be finalised in the SAP.

CCI [REDACTED]
 The number and the percentage of subjects CCI [REDACTED]

CCI [REDACTED]
 The CCI [REDACTED] total score and domain scores CCI [REDACTED] will be summarised at each visit by treatment group using descriptive statistics. Changes from baseline (Visit 2) will also be summarised for each post-baseline visit by treatment group. Scores will be computed according to the CCI [REDACTED] manual [18]. Multiple entries and missing data will be dealt with as described in the same manual.

CCI [REDACTED] will be analysed using a linear mixed model for repeated measures including treatment, visit, treatment-by-visit interaction, use of stable concomitant therapy with oral macrolides and pooled sites as fixed effects and baseline value as covariate. An unstructured covariance matrix will be assumed and the Kenward-Roger adjustment will be used for the degrees of freedom. The least square means in each treatment group, the least square mean differences between treatments, their 95% CIs and associated p-values at each visit will be estimated by the model.

The CCI [REDACTED] will be summarised and analysed similarly to the CCI [REDACTED]. Algorithm of scoring and methods for handling with multiple imputations and missing data will be performed according to the questionnaire instructions [20, 19].

CCI [REDACTED]

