- a worst case approach will be considered for duration of symptoms and requirement of hospitalisation. For example, if one of two exacerbations considered as a single episode has/have increased dyspnoea for ≥ 24 hours and < 48 hours and the other one has increased dyspnoea for ≥ 48 hours, the single episode will be considered in the analysis as having dyspnoea for ≥ 48 hours.

In order to investigate whether the use of inhaled colistimethate sodium reduces the frequency of pulmonary exacerbations compared to placebo in subjects with NCFB chronically infected with *P. aeruginosa*, the following hypothesis will be tested:

- Null hypothesis: there is no difference between inhaled colistimethate sodium and placebo as regards the effect on the pulmonary exacerbation rate
- Alternative hypothesis: inhaled colistimethate sodium reduces the pulmonary exacerbation rate in favour of inhaled colistimethate sodium compared to placebo.

The null hypothesis must be rejected for the efficacy of inhaled colistimethate sodium to be considered demonstrated.

The number and the percentage of subjects with NCFB pulmonary exacerbations, the number of NCFB pulmonary exacerbations and the total follow-up time in years, as defined in Section 4.1.7, will be summarised by treatment group.

The number of NCFB pulmonary exacerbations during the treatment period will be analysed using a negative binomial model including treatment, country, as detailed in Section 4.9.1, and use of stable concomitant therapy with oral macrolides as fixed effects and log-exposure time on treatment as an offset. The log-time on treatment in years will be calculated as $\ln(\text{exposure time})$.

The adjusted mean annual NCFB pulmonary exacerbation rates in each treatment group and the adjusted rate ratio with their 95% CIs will be estimated by the model. OBSMARGINS option will be used for the estimates. The number of subjects considered in the model will be provided by treatment group.

The number and the percentage of subjects with 0, 1, 2 or >2 pulmonary exacerbations will be presented.

The number and the percentage of subjects with pulmonary exacerbations, the number of pulmonary exacerbations will also be presented by treatment group for severe (defined as those requiring intravenous antibiotics and/or hospitalisation) and not severe exacerbations.

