4.7.6 Methods of Analysis for Secondary Endpoints

4.7.6.1 CCI [REDACTED]

The CCI [REDACTED] will be calculated as the time in days from the date of randomisation to the date at which the first pulmonary exacerbation occurs.

- CCI [REDACTED] (days) = start date of first NCFB pulmonary exacerbation - date of randomisation. (It should be noted that this differs slightly from the CCI [REDACTED] CCI [REDACTED] CCI [REDACTED] CCI [REDACTED]. For time-to-event endpoints, generally the + 1 is not included because this overestimates the time by 1 day for every event.)

Subjects completing the trial without CCI [REDACTED] or who are discontinued prematurely CCI [REDACTED], will be considered as censored at the time of their last follow-up, i.e. at the date of treatment completion/discontinuation. For the analysis, the following formula will be applied:

- Censoring time (days) = (date of treatment completion/discontinuation - date randomisation)

The number of subjects with a first CCI [REDACTED] events will be summarised.

CONFIDENTIAL

Sponsor:	Zambon S.p.A.	Protocol Number:	Z7224L02
----------	---------------	------------------	----------

A Cox proportional hazard regression model will be applied to the data to provide an estimate of the hazard ratio (HR), colistimethate sodium:placebo. The model will include treatment group, country, as detailed in Section 4.9.1, and use of stable concomitant therapy with oral macrolides as covariates. The HR and its associated 95% CI and p-value will be extracted from the model and presented. A supportive analysis will be conducted using the log-rank test and the associated p-value will be presented.

Kaplan-Meier estimates in each treatment group will be presented: median time to CCI, 25th and 75th percentiles and the corresponding CIs will be tabulated. The number of CCI-free subjects at the beginning of the period, the cumulative number of subjects with CCI at the end of the period and the estimated rates of pulmonary exacerbations at the end of the period with the associated 95% CIs will be presented by treatment group for the following study periods: (0-28] days, (28-90] days, (90-180] days, (180-270] days and (270 days - End of Treatment] as supportive statistics.

The estimate of the survivor function in each group will be displayed graphically using a Kaplan-Meier curve.

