4.9 Adjustment for Covariates

The adjusted mean annual NCFB pulmonary exacerbation rate will be estimated by a negative binomial model including treatment, use of stable concomitant therapy with oral macrolides (e.g. azithromycin or erythromycin or clarithromycin: Yes/No) and country, as detailed in Section 4.9.1, as fixed effects and log-time on treatment as an offset. An exploratory model will also be fitted considering the number of CCI requiring oral/intravenous antibiotics in the last 12 months prior to study entry.

The Cox proportional hazard regression model for CCI will include use of stable concomitant therapy with oral macrolides (e.g. azithromycin or erythromycin or clarithromycin: Yes/No) and country, as covariates.

In the analysis of CCI total score and CCI domain scores, a linear mixed model for repeated measures will be applied. This will include treatment, visit, treatment-by-visit interaction, use of stable concomitant therapy with oral macrolides (e.g. azithromycin or erythromycin or clarithromycin: Yes/No) and country, as fixed effects and baseline value as covariate.

The CCI CCI will be analysed by means of a linear mixed model for repeated measures including treatment, country, and use of stable concomitant therapy with oral macrolides (azithromycin or erythromycin or clarithromycin: Yes/No) as fixed effects and baseline value as covariate.

CONFIDENTIAL

Sponsor:	Zambon S.p.A.	Protocol Number:	Z7224L02
----------	---------------	------------------	----------

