4.13 Changes in Conduct or Planned Analyses from the Protocol

Sections 2.2, 4.4.11, 4.7.5 and 4.7.6.3: The protocol incorrectly referred to the units for the determination of CCI CCI which have been reported as CCI by the central laboratory.

Section 4.7.4: The protocol states that the Negative Binomial Model will consider the log-time on study as offset. However, as specified in Section 4.1.7, NCFB Pulmonary Exacerbations analyses focus on the treatment period so log-time on treatment will be considered.

Sections 4.7.5 and 4.7.6.1: The protocol states that the CCI
[REDACTED]
[REDACTED]. Using date of first IMP as the start time of risk is considered to be biased, so date of randomisation will be used instead.

CONFIDENTIAL

Sponsor:	Zambon S.p.A.	Protocol Number:	Z7224L02
----------	---------------	------------------	----------

Section 4.7.6.1: The protocol states that the CCI [REDACTED] CCI [REDACTED] For time-to-event endpoints, generally the + 1 is not included because this overestimates the time by 1 day for every event, therefore “+ 1” has been deleted.

Section 4.7.6.5: The protocol states that the CCI [REDACTED] total score will be computed and analysed. However, as recommended in the Manual Scoring Instructions [REDACTED], only the CCI [REDACTED] domain scores will be presented and analysed.

There have been no other changes in analyses from those defined in the protocol.

CONFIDENTIAL

Sponsor:	Zambon S.p.A.	Protocol Number:	Z7224L02
----------	---------------	------------------	----------

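### The SAP's primary model omits the prior-year exacerbation covariate named in the protocol synopsis, and the visible text of SAP 4.13 does not declare this

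*SAP*

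**What the plan says.** The Statistical Analysis part of the protocol synopsis (Section 3) compares annual exacerbation rates "using a Poisson regression model allowing for over-dispersion and also considering pooled site", and continues with "use of stable concomitant therapy with oral macrolides and pulmonary exacerbation frequency in the 12 months preceding Visit 2 as covariates".

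SAP 4.7.4 fits a "negative binomial model including treatment, country, as detailed in Section 4.9.1, and use of stable concomitant therapy with oral macrolides as fixed effects", with log exposure time as offset. SAP 4.9 and the GENMOD code in 4.14 give the same terms. Prior exacerbations appear in two other places:

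- SAP 4.9: "An exploratory model will also be fitted considering the number of" events treated with oral or intravenous antibiotics in the previous 12 months. The form of the term is not stated. The output is Table 14.2.1.1.6.
- SAP 4.1.5: a subgroup factor with levels 1, 2 and more than 2, formed by adding the recorded oral and intravenous counts.

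On the primary model, SAP 4.13 records only a change of offset: "The protocol states that the Negative Binomial Model will consider the log-time on study as offset". It closes with "There have been no other changes in analyses from those defined in the protocol".

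**The concern.** The synopsis and the SAP name different models for the one test that gates every secondary endpoint (SAP 4.7.5). The section meant to record such differences shows no entry for this one. SAP 4.9.1 explains why country replaces site, but no reason is given for moving the prior-year term to an exploratory model. The SAP is based on protocol version 5.0, the version supplied, so the difference does not come from superseded text.

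Prior exacerbation frequency is a natural predictor of later frequency. Leaving it out of a randomised comparison does not bias the test but gives up some precision. That matters a little more here because recruitment stopped at 287 of the planned 420 subjects (SAP 3.9).

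**Working it through.** **1. Terms side by side**

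| Element | Protocol synopsis | SAP primary model | Visible entry in SAP 4.13 |
|---|---|---|---|
| Distribution | Over-dispersed Poisson | Negative binomial | None as a change; the protocol is said to use a negative binomial |
| Site term | Pooled site | Country | None |
| Macrolide use | Yes | Yes | Not needed |
| Prior-year exacerbations | Yes | No (exploratory only) | None |

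The SAP's history variable also differs from the synopsis covariate. It counts oral and intravenous episodes before Screening (SAP 4.1.5, 4.4.3). The synopsis window ends at Visit 2, and inclusion criterion 4 also admits episodes treated with inhaled antibiotics.

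A further difference concerns a time-to-event endpoint. Protocol 19.4.2 says "A log-rank sum test will be used to compare the treatment groups". SAP 4.7.6.1 fits a Cox model, then adds "A supportive analysis will be conducted using the log-rank test and the associated p-value will be presented". No visible words in 4.13 list this, but its entries on that section are partly blacked out.

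**2. The plan's own power figures**

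Inputs from the synopsis: placebo rate 1.09 per year, 170 completers per arm, 1 year of follow-up, two-sided 0.05, 90% power at a 35% reduction and 80% at 30%. The dispersion k is redacted, so it is solved from

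Var(log RR) = (1/μ0 + 1/μ1 + 2k)/n, with k = ½[n(log RR)²/(z₀.₉₇₅ + z_power)² − 1/μ0 − 1/μ1].

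- 35% reduction, 90% power: ½[170 × 0.18557/10.507 − 0.9174 − 1.4114] = 0.337
- 30% reduction, 80% power: ½[170 × 0.12722/7.849 − 0.9174 − 1.3106] = 0.264

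One k does not give both figures exactly: k = 0.337 gives 77.9% at 30%, and k = 0.264 gives 91.4% at 35%. A value of 0.3 gives 90.7% and 79.0%. All of these fit the mild over-dispersion that the protocol describes.

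**3. Power at 287 subjects without the term**

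Take n = 143.5 per arm and RR = 0.65. Mean exposure t is assumed, because the trial stopped early.

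| Mean exposure (years) | Power, k = 0.337 | Power, k = 0.264 |
|---|---|---|
| 0.7 | 73.2% | 74.8% |
| 0.8 | 77.8% | 79.5% |
| 0.9 | 81.5% | 83.2% |

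**4. Gain from adding the term**

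If the covariate explains a fraction f of the heterogeneity, k becomes k(1 − f). The documents do not give f. Assume a gamma frailty shared by the prior-year and on-trial counts, restricted to subjects with at least two prior events (or one, with probability 0 to 0.2). A linear count then explains f = 0.127 to 0.209, and three categories explain 0.089 to 0.170.

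Worked case (t = 0.8, k = 0.3368, f = 0.209):

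- Without: (1.1468 + 1.7643 + 0.6736)/143.5 = 0.02498, SE 0.1581, power 77.8%
- With: (1.1468 + 1.7643 + 0.5328)/143.5 = 0.02400, SE 0.1549, power 79.4%
- The variance falls by 3.9% and power rises by 1.6 points.

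Over both values of k, the linear term adds 0.73–1.51 points at 0.7 year, 0.77–1.61 at 0.8 and 0.79–1.65 at 0.9. Variance falls by 1.7–4.3%. Three categories add 0.5–1.4 points.

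The gain would be larger if f were larger. At k = 0.3 and 0.7 year, power is 74.0% with f = 0, 75.7% with 0.25, 77.3% with 0.5 and 79.0% with 0.75.

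**5. Simulation check**

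Negative binomial fits were run on 19,650 trials per setting, each with 287 subjects and exposure uniform on 0.6 to 1.0 year. The models held treatment and the count only, without country or macrolide terms. At RR 0.65, 2.3–2.9% of trials were significant only with the linear term and 1.4–1.8% only without it, a net gain of 1.0 to 1.2 points. A pure-noise covariate gave about 1.1% disagreement with a net near zero, so gross disagreement overstates the effect. Under the null, rejection was 5.11–5.16% without the term and 5.13–5.19% with it.

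**The case against.** The strongest reply is that an undeclared change is shown only against a synopsis, which itself leaves full details to the SAP. The primary-model text of protocol 19.4.2 is not visible. SAP 4.13 attributes to the protocol a negative binomial model with a time-on-study offset, and the synopsis has neither, so the SAP authors were comparing with text that a reader cannot see. That text may omit the covariate. 4.13 would then be right on this point against the body, and the fault would be a mismatch between synopsis and body. This stands and limits the claim.

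The covariate is also not lost: the SAP has an exploratory model with its own table, and a subgroup analysis with an interaction test. The gain is about one power point and rests on a redacted dispersion and an assumed frailty model. Both points stand as limits on weight. They do not explain why a collected baseline count that the synopsis already names is left out of the primary model.

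The last objection is timing. It would be a late change to the primary model, after recruitment stopped on the sister trial's results. That is a real cost. It is acceptable only if the change is made and documented blind.

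**Conclusion.** The point holds as a modest one. Measured against the synopsis, the SAP's primary model drops a named covariate and the visible text of 4.13 does not say so. The cost is 0.7 to 1.7 power points for a 35% reduction, assuming k of 0.264 to 0.337, mean exposure of 0.7 to 0.9 year and 13 to 21% of heterogeneity explained.

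A reader might infer more than the documents support:

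- **That the primary result would be biased or its error rate inflated.** It would not. The covariate is measured before treatment, and the SAP's own model is unambiguous.
- **That 4.13 is wrong against the whole protocol on this covariate.** The visible text does not establish that.
- **That moving from Poisson to negative binomial is an undeclared change.** This is doubtful. Protocol 19.3 bases its power simulation on two negative binomials, and 4.13 says that the protocol specifies that model.
- **That the different windows matter much.** Inclusion criterion 4 bars exacerbations between Visits 1 and 2, so for eligible subjects the windows differ only at the far end, by the length of screening (nominally up to 45 days, longer with a Covid-19 extension).
- **That a recorded count of 0 should be raised to match inclusion criterion 4.** The protocol's change history says that the eligibility criteria were amended at version 4.0, during enrolment. The present wording is not a safe basis for overwriting recorded data.

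**What to change.** Before unblinding:

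1. Add the prior-year count, oral plus intravenous as defined in SAP 4.1.5, as a linear covariate to the primary model in 4.7.4, 4.9 and the GENMOD code in 4.14, and to the imputation model in 4.7.4.2 and its code.
2. Carry it into the analyses that follow the primary model: 4.7.4.1 (alternative definition), 4.7.6.4 and 4.7.6.8. In the subgroup run on prior count (4.7.4.3), the subgroup term replaces it.
3. Use the count as recorded, including 0. Fill missing history with the median pooled across arms on blinded data, so that no mITT subject is lost.
4. Keep the present SAP model as a sensitivity analysis.
5. Correct 4.13 to list the covariate's definition against the synopsis (oral and intravenous only, before Screening) and pooled site to country. Add log-rank to Cox if the redacted entries do not already cover it.
6. Reconcile the synopsis with unredacted protocol 19.4.2, including whether the negative binomial is a change at all.

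The cost is one degree of freedom, one missing-data rule, some SAP wording and a late change to the primary model that must be documented as made blind. Items 5 and 6 are needed whichever model is kept. Once the blind is broken, protocol 19.4 would make the model change post hoc, and only those two items would remain.
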